8.3.1 Datasets to be analysed

All retrospective data collected will be used for the main analysis. If some NH allocated to the intervention group do not hold the QC session but provide their data, they will be included in the analysis. The statistician performing the analysis will be blinded to the allocation; groups will be identified as A and B.

Subgroups analysis will be made, both for the primary and secondary outcomes, for the following subgroups:

- NH of Vaud;
- NH of Fribourg;
- NH with a geriatric mission;
- NH with a psychogeriatric mission;
- NH having held the QC session.

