5.3 Procedures

For clarity, the following section only describes activities planned for the first recruitment round. If a second round is necessary (see above), all activities will be held the following year in the NHs participating in this second round.

Randomisation:

Some responsible physicians work in multiple NHs; this could lead to contamination of the control group. Moreover, some NHs have multiple responsible physicians; these two factors lead to the apparition of clusters of physicians working in the same NHs and which could amplify contamination of the control group. To account for this factor, after inclusion and before randomisation, NHs will be clustered by physicians: all NHs sharing at least one physician will be placed in the same cluster. NHs sharing no physician with another will be placed in clusters of size one.

A random list of A (intervention) and B (control) will be used to allocate NHs clusters to groups. The list will be constructed by generating a random list of numbers comprised between 0 and 1, with uniform distribution; numbers below 0.5 will be assigned the letter A, the others the letter B. The list will be of the same length as the list of included NHs clusters, and will be generated using Stata version 14.1.

Given the variable size of the clusters, this may lead to the constitution of two groups of unequal size. However, given the relatively small size of expected clusters (the largest possible cluster we are aware of regroups eight NH; most clusters will only include two NHs), this should not lead to a dramatic unbalance between the two groups.

Intervention:

Pharmacists of the NHs assigned to the intervention group will take part in a course where the material for the quality circle module (slides, relevant scientific literature and guidelines) will be made available to them. The content of the course was developed at the CPC. It comprises an overview of the problems posed to older people by polypharmacy and the use of PIMs, an in-depth description of the process of deprescribing and of the challenges to enacting it, a selection of useful clinical tools, and a selection of guidelines to deprescribe specific therapeutic classes (for example, proton-pump inhibitors or cholesterol-lowering drugs).

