5.4 Methods of minimising bias

To account for the other influences on the prescribing practices of physicians, a controlled design has been chosen. Thus, external influence from medical literature, expert opinions, treatment guidelines or other sources should equally impact NHs in the intervention and control groups.

Randomisation will increase the likelihood that the characteristics of participating NHs are similar between the two groups. To account for the fact that some physicians are responsible for more than one NH, thus allowing for "bleeding" of the intervention between the two groups, randomisation will be clustered at the physician level (see section 5.3, page 13 for details).

Previous discussions with the prospective participants and their professional associations show that there is a great interest for deprescribing among partners. We fear that a purely controlled design will prevent the participation of some of the most interested NHs, thus minimising the effect of the intervention. To reduce this risk, we will offer the possibility to participants randomized to the control group to enact the intervention one year after the start of the study. At this point, all NH in the intervention group will have submitted to the intervention and its effects will have full deployed.

Finally, assessments of the study outcomes will be conducted while maintaining allocation blinding, ensuring that no analysis bias occurs.

Given that the unit of analysis is the NH, the risk of loss to follow-up is deemed inexistent. Data collection will take place in the same way as it already routinely does in a satisfactory way, thus reducing the risk of missing data.

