## Statistical analysis

---

The treatment groups were randomly allocated among nursing-homes (NH). The analyst will be blinded with regard to the allocation.

Analyses will be performed at NH level, the NH being the unit of analysis (i.e. there is one data point per NH per variable).

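### The plan does not secure the analyst blinding it claims: the groups are labelled A and B, letters that section 5.3 has already defined as intervention and control

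*Protocol*

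**What the plan says.** Three places claim that the analysis is blinded.

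- Protocol section 8.3.1 says that the statistician will not know the allocation and that "groups will be identified as A and B".
- Protocol section 5.4: "assessments of the study outcomes will be conducted while maintaining allocation blinding, ensuring that no analysis bias occurs".
- SAP, Statistical analysis: "The analyst will be blinded with regard to the allocation".

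Only section 8.3.1 names a device, the two letters. Section 5.3 gives those letters a meaning at randomisation: "A random list of A (intervention) and B (control) will be used to allocate NHs clusters to groups". It then explains how the list is drawn: "numbers below 0.5 will be assigned the letter A, the others the letter B".

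Section 8.3.1 also lists the subgroups to be analysed. The last one is "NH having held the QC session".

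**The concern.** A pair of letters hides the arms only if the reader does not know what they stand for. Here the protocol prints their meaning, and nothing in either document keeps the protocol from the statistician. If the analysis file carries the randomisation letters, the statistician can read off the arms.

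What is at stake is the set of judgements that come before the primary p-value. Under Inferential analysis, the SAP asks the analyst to decide:

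1. whether the outcome is close enough to normal;
2. whether the variances are equal;
3. which distribution and link to use if it is not normal;
4. whether any acceptable model exists. If none does, the comparison becomes a Mann-Whitney test with no baseline adjustment.

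Under Data preparation, the SAP names a histogram, skewness and kurtosis for the normality check but gives no cut-offs. An analyst who knows the arms could, even without intending to, favour the option that moves the estimate in the hoped-for direction. Blinding is meant to limit that, and section 5.4 relies on it for a strong claim.

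**Working it through.** No arithmetic applies. The point concerns group labels and does not depend on sample size, effect size or error rates. The check is to set the texts side by side.

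**Step 1: the letters.** Section 5.3 makes A intervention and B control. Section 8.3.1 gives the statistician groups called A and B. The letters are not redefined between the two sections.

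**Step 2: is a recoding step described anywhere?** None is found in either document. The SAP states that the analyst is blinded but gives no labels, no recoding and no key holder. Its Data preparation section says only that the data reach the statistician as an Excel file. Sections 9.1 and 9.3 do mention a coding key, but it covers the nursing-home data and not the arm labels.

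**Step 3: could the statistician have the protocol?** Neither document says it is withheld. The SAP's section on secondary outcomes follows protocol section 8.2 almost word for word, including the slip by which the restraint paragraph speaks of falls. Whoever wrote the SAP therefore worked from the protocol text. The documents do not say whether that person also runs the analysis.

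**Step 4: the QC-session variable.** Section 5.1 assigns the session to intervention homes. Section 5.4 offers it to control homes one year after the start. Within the follow-up year, a home recorded as having held the session is therefore an intervention home under the plan, whatever label its group carries. The reverse does not follow, because section 8.3.1 allows for intervention homes that never hold the session. One positive record is enough to identify the group. The leak depends on timing: it matters only if the variable arrives before the primary models are fixed. The protocol does not say when it is supplied, and the SAP lists neither this variable nor any subgroup analysis.

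**Step 5: what blinding would protect.** Fit and normality can be judged without knowing which group is which. An analyst holding neutral codes still sees a two-sided p-value under each candidate model. Neutral codes therefore limit steering towards a favoured arm, but they do not prevent choosing among models for significance. Only prespecified rules do that.

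**The case against.** The strongest reply is that A and B are ordinary neutral labels. Section 8.3.1 says in the same sentence that the statistician is blinded, and no text says the randomisation letters are carried into the analysis file. Someone prepares the spreadsheet for the statistician and could swap or redraw the labels. The SAP never uses the letters at all.

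This stands as a limit on what can be claimed. A reader might infer that the blinding does not exist, or that the analyst is certain to know the arms. The documents do not support either statement. They do not show that the two sets of letters share a key, and an unwritten recoding step could restore the blinding. The reply does not show that such a step is planned.

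A second reply is that practical exposure is limited. The primary outcome is a ratio at nursing-home level, built from routine consumption data with a screening tool and a database lookup, so the statistician does not judge individual outcomes. That also stands, and it largely disposes of measurement bias through the analyst. It does not touch the model choices.

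A third reply is that the open model selection in the SAP is the real weakness and that recoding would not cure it. That is right. A reader might infer that the choices are safe once the analyst is blinded, or that blinding is their only protection. Neither holds, as step 5 of the working shows.

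**Conclusion.** The plan as written does not secure the analyst blinding it claims. Its only stated device is a pair of labels that the protocol itself decodes, with no recoding described in either document. The QC-session variable is a second, conditional route to the same information.

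The size of any resulting bias cannot be computed from the documents, and none is asserted. The conclusion assumes that the statistician can read the protocol and that no undocumented relabelling takes place. If relabelling is in fact planned, the defect is one of documentation only. The point is worth correcting because section 5.4 relies on blinding to exclude analysis bias and the SAP leaves several choices open until the data have been seen.

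**What to change.** In section 8.3.1 and in the SAP's Statistical analysis section, state that:

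- a designated person outside the analysis team replaces the arm labels with two new, randomly drawn neutral codes that were not used at randomisation, and holds the key;
- the key and the QC-session variable are released only after the primary and co-primary models are locked, so the QC-session subgroup is run after that. The SAP lists no co-primary outcome, so the lock must name it explicitly.

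Before naming the custodian, reconcile sections 9.1 and 9.3. Section 9.1 places the existing coding key with a quality office that is not part of the project. Section 9.3 says the key is out of reach of anyone outside the investigators' own centre (the CPC). Both cannot hold if that office is outside the centre.

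The cost is a sentence or two in each document, the reconciliation of those two sections, and a few minutes of recoding. Tightening the model-selection rules is a separate task that this change does not replace.

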Project assessments, procedures:	Participating NHs will be randomised in two groups. NHs allocated to the intervention group will hold a QC session on deprescribing, where a local consensus on the deprescribing of specific therapeutic classes will be elaborated.									
	The effects will be assessed using anonymous data on the drug consumption of the NH (already routinely collected for the administrative monitoring of the pharmaceutical assistance programme) and NH-level data on falls, hospitalisation, emergency events and death. The implementation outcomes will be evaluated with questionnaires to health care professionals of the intervention group at baseline, 3 months and 12 months.									
Number of Participants:	62 NHs will be included in this project, 31 in each group (intervention and control). Assuming a normal distribution of the reduction in PIMs proportion and a standard deviation of 7.5%, similar between the two groups, this number of participant will allow for the detection of a 20% relative reduction in the primary outcome, from 22.8% to 18.2%, with 80% power.									
Project Duration:	From December 2017 to March 2019 (possible extension to March 2020)									
Project Centre(s):	Single-centre; the intervention will take place in multiple NHs in the cantons of Vaud and Fribourg.									
Statistical Considerations:	The inclusion of 62 NH will allow for the detection of a 20% relative reduction in the use of PIMs with 80% power.									
	The main outcome will be assessed using a generalised linear regression model taking the difference at 12 months in overall PIM proportion as dependent variable. The secondary outcomes will be assessed using the same methodology. The 5% level of significance will be considered for all analyses.									
Other methodological Considerations:	No other methodological considerations.									
Risk-Benefit statement:	In previous studies of deprescribing in older people residing in nursing homes, very few adverse events occurred, none of them serious. Moreover, physicians will retain complete control over NH residents' treatments during the study. It is thus estimated that the intervention poses little to no risk compared to usual care. Possible benefits include a reduced mortality rate and fewer adverse drug reactions, as well as fewer hospital stays and reduced consumption of acute care. The risk-benefits balance of this project is estimated to be clearly positive.									

ABBREVIATIONS

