8. STATISTICAL METHODOLOGY

8.1 Determination of sample size

Based on the retrospective data collected for the administrative monitoring of the Fribourg PAP, the mean proportion of PIM in the NH of Fribourg in 2015 was 22.8% (SD 6.3%). The natural year-on-year variation of the outcome was calculated between 2014 and 2015: the mean difference is 0.8% (IC₉₅ -1.1% - 2.7%, SD 5.3%); the correlation coefficient ρ between values of the outcome for 2014 and 2015 is 0.54 (IC₉₅ 0.29 – 0.72).

Studies of deprescribing have shown relative reductions in the number of PIMs ranging from 6.4% [33] to 31%[34]; one of the largest studies so far showed a 19.7% reduction in the number of PIMs [30]. Our hypothesis is that the intervention proposed in this study will reduce the proportion of PIMs used by 20%, in relative term.

We aim to detect an absolute difference of 4.6% ($22.8\% \times 0.2$) in the one-year reduction of the proportion of PIM between the control and intervention groups. The standard deviation of the difference at 12 months (SD_{diff}) was estimated with the following formula, assuming that the standard deviation at baseline and 12 months were the same and equal to 6.3%:

$$Var_{diff} = Var_{baseline} + Var_{12\;months} - 2 \cdot \rho \cdot SD_{baseline} \cdot SD_{12\;months}$$

By varying the correlation coefficient ρ along the confidence interval, plausible values of SD_{diff} were estimated to be between 4.1% (ρ =0.7) and 7.5% (ρ =0.3). A value of ρ =0.3 (SD_{diff} = 7.5%) was chosenas a conservative estimate for the calculation of the sample size, given the moderate correlation between the values for 2014 and 2015. To detect a difference between a mean difference of 0 in the control group and 4.6 in the intervention group (common SD of 7.5%, risks of α and β errors of 5% and 20%), 66NH, 33 per group, will have to be included. With an optimistic estimate of ρ = 0.7, the number of NH to include would decrease to 36. However, as this could lead to a lack of statistical power, a conservative estimate has been preferred.

Given that 82 NH meet inclusion criteria in the canton of Vaud and 42 in the canton of Fribourg, we expect that approximately 2/3 of the participants will be recruited in Vaud, and 1/3 in Fribourg.

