8.3 Planned analysis

Descriptive statistics

Participating NH will be described, by group, in terms of number of beds, mean age of residents, mission (geriatric, psycho-geriatric or mixed), and number of nurses, physicians and pharmacists. Each implementation outcome (list available in Annex 1) will be presented with a suited summative data.

Inferential statistics

The main outcome is the difference in the overall proportion of PIMs used in the NH 12 months after intervention, relative to baseline. The primary analysis will test the difference in the overall proportion of PIMs between the intervention and control groups using a generalised linear regression model, taking the difference in overall proportion of PIMs at 12 months as the dependant variable, and the group allocation (binary variable) and baseline overall proportion of PIMs as independent variables (two-sided α = 0.05). The analysis will be made immediately after the completion of follow-up data collection.

The same analysis will be carried out for the co-primary outcome, with the overall number of potentially inappropriate DDD at 12 months as dependent variable, adjusted for baseline value, taking into account the group allocation.

Generalised linear models will also be used to assess differences in secondary outcomes between the two groups will be tested with the same method as the primary outcome, taking the baseline value and the group allocation as the independent variables, with two-sided $\alpha = 0.05$. If enough supplementary data on falls and hospitalisations are available (see section 7.3 page 19), they will be analysed as the number of falls, respectively the number of hospital days, per mean resident and per year.

All analyses will be made using the Stata statistical package (StataCorp LP, College Station, TX, USA).

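### Cantons and missions are listed as separate subgroup analyses with no interaction test; if the planned effect is the same in both cantons, about half of trials would be significant in exactly one

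*Protocol*

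**What the plan says.** Protocol section 8.3.1 reads: "Subgroups analysis will be made, both for the primary and secondary outcomes, for the following subgroups". Five sets follow: Vaud, Fribourg, geriatric mission, psychogeriatric mission, and homes that held the quality circle session. The co-primary outcome is not named in that sentence.

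The synopsis, under Statistical Considerations, adds: "The 5% level of significance will be considered for all analyses".

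The only models described are in Protocol section 8.3. For the primary outcome the covariates are "the group allocation (binary variable) and baseline overall proportion of PIMs as independent variables (two-sided α = 0.05"). Secondary outcomes are handled by "taking the baseline value and the group allocation as the independent variables". No canton, mission or interaction term appears.

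On the size of the subgroups, section 8.1 expects that "approximately 2/3 of the participants will be recruited in Vaud, and 1/3 in Fribourg". No subgroup size or power is given.

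The SAP's section on inferential analysis contains no subgroup analysis, so it neither specifies nor limits what the protocol announces.

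**The concern.** Finding p below 0.05 in one subgroup and above 0.05 in the other does not test whether the effect differs between them. When each subgroup has modest power, that pattern is common even if the effect is the same in both.

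Here a canton-level contrast could matter. The two cantons run separate pharmaceutical assistance programmes, and section 3.2 says the project is meant to inform policy makers. A result significant in Vaud only could be taken to mean that the module works there and not in Fribourg. The same could happen with falls, mortality, restraint and hospital days, which are secondary outcomes and so fall within the subgroup plan.

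**Working it through.** **Inputs**
- Effect (Protocol 8.1): "We aim to detect an absolute difference of 4.6" percentage points.
- Spread (8.1): "common SD of 7.5%, risks of α and β errors of 5% and 20"%. The 7.5 comes from a correlation of 0.3, "assuming that the standard deviation at baseline and 12 months were the same and equal to 6.3"%. The observed correlation is 0.54 (0.29 to 0.72).
- Test (8.3): two-sided, 0.05.
- Size: 62 homes in the synopsis, 66 in section 8.1. Both are used below.
- Split (8.1): two thirds Vaud, one third Fribourg. With 62 homes this is about 41 (21 against 20) and 21 (10 against 11). With 66 it is 22 and 11 per arm.

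**The plan's own sample size.** Per arm, n = 2(z₁₋α + z₁₋β)² SD²/d².
- One-sided: 2 × (1.645 + 0.842)² × 7.5²/4.6² = 32.9, so 33 per arm and 66 in all. This matches section 8.1.
- Two-sided, with 1.960 in place of 1.645: 41.7, so 42 per arm and 84 in all.

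Under the two-sided test that section 8.3 specifies, whole-trial power without baseline adjustment is 70% with 66 homes and 67.5% with 62. This is a separate matter, but it means the subgroups start from less than 80%.

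**Power within each canton, unadjusted, 62 homes.** SE = 7.5 × √(1/n₁ + 1/n₂).
- Vaud: SE = 7.5 × √(1/21 + 1/20) = 2.34; 4.6/2.34 = 1.96; noncentral t power 48.2%.
- Fribourg: SE = 7.5 × √(1/10 + 1/11) = 3.28; 4.6/3.28 = 1.40; power 26.6%.

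P(exactly one significant) = p₁(1 − p₂) + p₂(1 − p₁) = 0.482 × 0.734 + 0.266 × 0.518 = 0.354 + 0.138 = **49%**. With 66 homes it is 50.5%.

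**With the planned baseline adjustment.** Residual SD = 6.3 × √(1 − ρ²). Common effect 4.6 points, 62 homes:

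| ρ | Residual SD | Vaud power | Fribourg power | Exactly one significant |
|---|---|---|---|---|
| 0.3 | 6.01 | 67% | 38% | 54% |
| 0.54 | 5.30 | 77% | 47% | 52% |
| 0.7 | 4.50 | 89% | 60% | 42% |

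A 10,000-run simulation of the adjusted model with 66 homes gave 54%, 52% and 42%.

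**Smaller common effects**
- 2.3 points: 23% unadjusted (62 homes), 30% adjusted at ρ = 0.3 (62 homes), 36% adjusted at ρ = 0.54 (66 homes).
- No effect: 2 × 0.05 × 0.95 = 9.5%.

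**What drives it.** With an equal split of 31 homes per canton, the unadjusted figure at 4.6 points is still 47% (50% adjusted at ρ = 0.3). Low power within each canton is the main cause; the unequal split adds little.

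**What an interaction test would do.** In the simulations with the same effect in both cantons it rejected in about 5% of trials. Its power is limited. With 66 homes and SD 7.5, SE = 7.5 × √(2/22 + 2/11) = 3.92. Power for a 4.6-point difference between cantons is about 22%, and about 11 points (2.80 × 3.92) would be detectable with 80% power. With residual SD 6.01 (ρ = 0.3) the SE is 3.14 and power about 31%.

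**The case against.** Section 8.3.1 lists subgroups; it gives no subgroup model and does not plan to compare p-values or to claim effect modification. The 5% level comes from a general sentence in the synopsis. Pre-specified subgroup estimates are legitimate, and nothing prevents reporting them with confidence intervals. This stands in part. Separate testing is an inference, though it is the natural reading of single-category sets under a heading about datasets, with two-term models and one significance level for everything. How readers would interpret the results is a prediction and not something the plan says.

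Three stronger readings are tempting, and the documents do not support them:
- That one-canton significance is expected about half the time whatever the effect. It holds only near the planned 4.6 points. That value is a hypothesis; section 8.1 cites relative reductions from 6.4% to 31%.
- That the cantons would show opposite results. The figure counts significance in one canton only. Estimates of opposite sign would occur in about 10% of trials at 4.6 points and SD 7.5 (5% adjusted at ρ = 0.3).
- That such a result simply reflects Vaud's larger size. About 14 of the 49 percentage points are significance in Fribourg only.

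The interaction test's low power is also a fair objection to relying on its p-value. It is no argument for separate tests; it is the reason to rest on estimates and intervals.

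**Conclusion.** The concern holds in a conditional form. If the planned 4.6-point effect is identical in both cantons, the primary outcome would be significant in exactly one of them in about 49% of trials at SD 7.5, and in about 52 to 54% with baseline adjustment at a correlation of 0.54 to 0.3 (42% at 0.7). Neither document has an interaction test, an exploratory label or a rule of interpretation to guard against misreading this. The choice between 62 and 66 homes changes the figures by only one or two percentage points.

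The calculation assumes independent homes and arms balanced within canton. Section 5.3 allocates physician clusters, of up to eight homes, by simple randomisation without stratification by canton, which could lower subgroup power further.

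The mission subgroups raise the same problem, but their sizes are not given, so no figure is offered. Mixed-mission homes are recorded (section 5.3) but are not a listed subgroup. The session-held set is different in kind: it is defined after randomisation and only in the intervention arm, so no interaction with allocation can address it.

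This is a desirable improvement. The primary conclusion does not depend on it.

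**What to change.** Change Protocol section 8.3.1 and add a subgroup paragraph to the SAP:
- Replace the separate canton and mission tests with allocation-by-canton and allocation-by-mission interaction terms in the baseline-adjusted model. Enter mission with its three collected categories (geriatric, psychogeriatric, mixed).
- Do this for the primary outcome, the co-primary outcome and any secondary outcome kept for subgroup analysis.
- Report each subgroup estimate with a 95% confidence interval and the interaction p-value. Make no within-subgroup significance claims, and label the results exploratory.
- Call the set of homes that held the session a non-randomised per-protocol sensitivity analysis, not a subgroup.

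The cost is wording in both documents and a few extra model runs, with no new data. The downside is the low power of the interaction test, which the confidence intervals will show openly.
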